## Statistical Analysis Plan Template

Sponsor:	ProQR Therapeutics		
Protocol:	PQ-110-002		
Document Version No.:	1.0	Document Date:	04 JAN 2022

### Composite Score Calculation

To calculate an overall composite score for the VFQ-25, simply average the visiontargeted subscale scores, excluding the general health rating question. By averaging the sub-scale scores rather than the individual items we have given equal weight to each sub-scale, whereas averaging the items would give more weight to scales with more items.

**Table 6. Scoring Key: Recoding of Items**

Item Numbers	Change original response category(a)	To recoded value of:
1,3,4,15c(b)	1 2 3 4 5	100 75 50 25 0
2	1 2 3 4 5	100 80 60 40 20 0
5,6,7,8,9,10,11,12,13,14,16,16a A3,A4,A5,A6,A7,A8,A9(c)	1 2 3 4 5 6	100 75 50 25 0 *
17,18,19,20,21,22,23,24,25, A11a,A11b,A12,A13	1 2 3 4 5	0 25 50 75 100
A1,A2	0 To 10	0 To 100

(a) Precoded response choices as printed in the questionnaire.

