### 4.8.8. VFQ-25/CVAQC

The observed value and change from baseline values over time for overall VFQ-25 composite scores for adult subjects and CVAQC scores for pediatric subjects will be summarized by treatment group and visit for the Efficacy Evaluable Population and Per Protocol Analysis Set using descriptive statistics. Descriptive summaries of VFQ-25/CVAQC for the subpopulations of subjects defined in Section 4.2.7 will also be provided. Subject level listings will be produced.

- **VFQ-25** Scoring VFQ-25 is a two-step process:

**Step 1:** original numeric values from the survey are re-coded following the scoring rules outlined in Table 6. All items are scored so that a high score represents better functioning. Each item is then converted to a 0 to 100 scale so that the lowest and highest possible scores are set at 0 and 100 points, respectively. In this format scores represent the achieved percentage of the total possible score, e.g. a score of 50 represents 50% of the highest possible score.

**Step 2:** items within each sub-scale are averaged together to create the 12 subscale scores. Table 7 indicates which items contribute to each specific sub-scale. Items that are left blank (missing data) are not taken into account when calculating the scale scores. Sub-scales with at least one item answered can be used to generate a sub-scale score. Hence, scores represent the average for all items in the subscale that the respondent answered.

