## Statistical Analysis Plan Template

Sponsor:	ProQR Therapeutics		
Protocol:	PQ-110-002		
Document Version No.:	1.0	Document Date:	04 JAN 2022

(b) Item 15c has four-response levels, but is expanded to a five-levels using item 15b.

Note: If 15b=1, then 15c should be recoded to "0"

If 15b=2, then 15c should be recoded to missing.

If 15b=3, then 15c should be recoded to missing.

(c) "A" before the item number indicates that this item is an optional item from the Appendix. If optional items are used, the NEI-VFQ developers encourage users to use all items for a given subscale.

This will greatly enhance the comparability of sub-scale scores across studies.

\* Response choice "6" indicates that the person does not perform the activity because of non-vision related problems. If this choice is selected, the item is coded as "missing."

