**Table 7. Averaging of Items to Generate VFQ-25 Sub-Scales**

Scale	Number of Items	Items to be averaged (after recoding per previous Table)
General Health	1	1
General Vision	1	2
Ocular Pain	2	4, 19
Near Activities	3	5, 6, 7
Distance Activities	3	8, 9, 14
Vision Specific:		
Social Functioning	2	11, 13
Mental Health	4	3, 21, 22, 25
Role Difficulties	2	17, 18
Dependency	3	20, 23, 24
Driving	3	15c, 16, 16a
Color Vision	1	12
Peripheral Vision	1	10

- **Cardiff Visual Ability Questionnaire for Children (CVAQC)-25**

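### SAP Table 6 gives VFQ-25 item 2 five response codes but six recoded values, so a score of 0 cannot be reached and the row must be reconciled with the questionnaire

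*SAP*

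**What the plan says.** VFQ-25 is the patient-reported secondary endpoint for adults (protocol 4.1.2, SAP 2.5.2.1). SAP 4.8.8 scores it in two steps.

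- **Step 1** recodes each answer through Table 6 so that "the lowest and highest possible scores are set at 0 and 100 points". The codes in Table 6 are described as "Precoded response choices as printed in the questionnaire". For item 2 the table prints codes 1, 2, 3, 4, 5 and recoded values "100 80 60 40 20 0".
- **Step 2** averages items into sub-scales. "Items that are left blank (missing data) are not taken into account when calculating the scale scores", and "Sub-scales with at least one item answered can be used to generate a sub-scale score". In Table 7 the "General Vision" sub-scale consists of item 2 alone.
- **Composite:** the instruction is to "simply average the visiontargeted subscale scores, excluding the general health rating question". Table 7 has 12 sub-scales, so 11 remain.

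SAP section 5, on changes to planned analyses, mentions no change to VFQ-25 scoring.

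**The concern.** A recoding key has to pair each response with one score. The item 2 row does not. It has one more value than it has codes, and the value left over is the 0 that Step 1 requires as the minimum. Either a response code is missing from the list or the list of values belongs to a scale with a different number of levels.

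The row feeds the endpoint directly. General Vision has no second item to fall back on, so an item 2 answer without a score removes the sub-scale and the composite is averaged over the rest. The affected answer would be the worst one, so any error would push scores upward at the poor end of the scale. SAP 4.8.8 also asks for VFQ-25 summaries in the section 4.2.7 subpopulations, which include on-chart versus off-chart subjects. An error at the floor would matter most in the off-chart group.

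**Working it through.** **1. Count codes and values in Table 6.**

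| Items | Codes | Values |
|---|---|---|
| 1, 3, 4, 15c | 5 | 5 |
| 2 | 5 | 6 |
| 5 to 14, 16, 16a | 6 | 6 (the last is the missing marker) |
| 17 to 25 | 5 | 5 |

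Item 2 is the only row with listed codes that does not balance.

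**2. Try to reproduce the plan's own minimum.** Step 1 says 0. Pairing item 2 in printed order gives 1→100, 2→80, 3→60, 4→40, 5→20, with 0 unpaired. The lowest reachable score is 20, so the stated minimum is not reproduced.

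**3. Reading A: a sixth code was omitted.** Six equally spaced values from 100 to 0, together with the 0-to-100 rule, favour this reading. Let M be the mean of the other 10 vision-targeted sub-scales. The documents do not give M, so the range below is an assumption. With all 11 sub-scales otherwise available:

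- item 2 scored 20: composite = (10M + 20)/11
- sixth answer scored 0: composite = 10M/11
- sixth answer treated as missing: composite = M

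Treating it as missing overstates the composite by M − 10M/11 = M/11. For a subject who moves from 20 to the sixth answer, with the other sub-scales unchanged, the composite changes by (M − 20)/11 instead of −20/11 = −1.82.

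| M (assumed) | Overstatement, M/11 | Change if missing, (M − 20)/11 | Change if scored 0 |
|---|---|---|---|
| 10 | 0.91 | −0.91 | −1.82 |
| 20 | 1.82 | 0.00 | −1.82 |
| 30 | 2.73 | +0.91 | −1.82 |
| 40 | 3.64 | +1.82 | −1.82 |
| 50 | 4.55 | +2.73 | −1.82 |
| 70 | 6.36 | +4.55 | −1.82 |

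If Driving cannot be scored either, the divisor is 10. The overstatement is then 3.0 at M = 30 and 5.0 at M = 50, and the properly scored change is −2.0.

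If the other sub-scales fall by d points on average at the same time, the composite still rises only when d < (M − 20)/11, that is 0.91 at M = 30 and 2.73 at M = 50.

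One such subject among n adults shifts a group mean by M/(11n). At M = 50 this is 50/55 = 0.91 for n = 5 and 50/121 = 0.41 for n = 11 (n assumed; the protocol maximum for the whole study is 11).

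**4. Reading B: item 2 has only five choices.** Five even levels over 0 to 100 would be 100, 75, 50, 25, 0, as in the row for items 1, 3, 4 and 15c. Against that scale the printed values over-score codes 2 to 5 by 5, 10, 15 and 20 points. With all 11 sub-scales scored, that adds 0.45, 0.91, 1.36 and 1.82 points to the composite.

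**The case against.** **The questionnaire is not in the documents.** Nothing there shows that item 2 has six choices, so an unscored worst answer is an inference. This stands. It does not rescue the row, because under the five-choice reading the values are wrong.

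**No SAP rule sends such an answer to missing.** The Step 2 rule covers items left blank, and a sixth answer is not blank. The footnote that codes response 6 as missing belongs to the starred row and describes activities not performed for reasons unrelated to vision. A programmer who sees a final 0 in the row and the 0-to-100 rule could well score the sixth answer 0. This also stands, and the amounts under reading A depend on the program having done otherwise.

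**A reader might infer that the composite goes up when a subject's vision gets worse.** The documents do not support that as a general statement. It needs a sixth answer, treated as missing, with M above 20 and the other sub-scales falling by less than (M − 20)/11. At M = 20 or below there is no rise, although the score is still overstated.

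**A reader might also infer that the enrolled subjects are known to be at light perception and so would use the worst answer.** SAP 4.8.1.2 only defines responder categories, and 4.8.1 only says how such data can be collected. Neither shows an enrolled eye at that level, and VFQ-25 is scored per subject, not per eye.

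**A digit may have been lost when the PDF was read.** This cannot be excluded, although the final 6 and asterisk in the following row survived. The source should be checked first.

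**Conclusion.** As printed, the item 2 row conflicts with the SAP's own 0-to-100 rule and does not give a correct key whether a code is missing or a value is surplus. An omitted sixth code is the likelier explanation but is not established. How far results are affected depends on the true number of choices, on what the program does with an answer outside 1 to 5, and on M.

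Severity is minor to moderate. The primary endpoints are adverse events, the analyses are descriptive, and VFQ-25 is one of several secondary endpoints. No output is shown to be affected. It still needs correcting, because the rule defines the score for a named endpoint and, with so few subjects, one mis-scored answer can be visible in a group mean.

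**What to change.** 1. Check the item 2 row of Table 6 in the source PDF. If a sixth code is printed there, the point closes.
2. Otherwise reconcile the row with the printed questionnaire so that codes and values match one to one and span 0 to 100. If item 2 has six choices, list codes 1, 2, 3, 4, 5, 6 against 100, 80, 60, 40, 20, 0. If it has five, replace the values with a five-level set.
3. Check how the VFQ-25 program scores item 2, including any answer outside 1 to 5, and rerun any General Vision or composite output that used a wrong mapping.

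The cost is one table cell and a program check. No new data are needed.

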## Statistical Analysis Plan Template

Sponsor:	ProQR Therapeutics		
Protocol:	PQ-110-002		
Document Version No.:	1.0	Document Date:	04 JAN 2022

(b) Item 15c has four-response levels, but is expanded to a five-levels using item 15b.

Note: If 15b=1, then 15c should be recoded to "0"

If 15b=2, then 15c should be recoded to missing.

If 15b=3, then 15c should be recoded to missing.

(c) "A" before the item number indicates that this item is an optional item from the Appendix. If optional items are used, the NEI-VFQ developers encourage users to use all items for a given subscale.

This will greatly enhance the comparability of sub-scale scores across studies.

\* Response choice "6" indicates that the person does not perform the activity because of non-vision related problems. If this choice is selected, the item is coded as "missing."

**Table 7. Averaging of Items to Generate VFQ-25 Sub-Scales**

Scale	Number of Items	Items to be averaged (after recoding per previous Table)
General Health	1	1
General Vision	1	2
Ocular Pain	2	4, 19
Near Activities	3	5, 6, 7
Distance Activities	3	8, 9, 14
Vision Specific:		
Social Functioning	2	11, 13
Mental Health	4	3, 21, 22, 25
Role Difficulties	2	17, 18
Dependency	3	20, 23, 24
Driving	3	15c, 16, 16a
Color Vision	1	12
Peripheral Vision	1	10

- **Cardiff Visual Ability Questionnaire for Children (CVAQC)-25**

## Statistical Analysis Plan Template

Sponsor:	ProQR Therapeutics		
Protocol:	PQ-110-002		
Document Version No.:	1.0	Document Date:	04 JAN 2022

CVAQC-25 is a visual impairment ability questionnaire for children with 25 items. The response to each item has 5 categories. In this study, the CVAQC-25 total score will be calculated using “Rasch” scoring algorithm. Based on this method, each item has a base measure which calls Item Measure (Table 8), and each category of response has a measure which calls Category Measure (Table 9). To calculate the total score following steps will be taken:

- 1- For each item, Item Score will be calculated as sum of Item Measure and its Category Measure
- 2- CVAQC-25 total score will be calculated as average of none missing item scores

**Table 8 CVAQC-25: Item Measure**

Item No.	Item	Item measure
1	Maths Lessons	0.33
2	Science Lessons	-0.25
3	Geography	-0.86
4	Language	0.06
5	Text books/Work sheet	-0.19
6	Smallest print	-2.18
7	Drawing/colouring/ Painting	0.77
8	Mobile phone	0.10
9	Restaurant menus	-0.79
10	Board in your classroom	-0.76
11	Television	1.30
12	Film at the cinema	1.45

**Table 9 CVAQC-25: Category Measure**

Category measures	
1	-2.96
2	-0.85
3	0.95
4	2.8
5	Missing data

## Statistical Analysis Plan Template

Sponsor:	ProQR Therapeutics		
Protocol:	PQ-110-002		
Document Version No.:	1.0	Document Date:	04 JAN 2022

13	Day light	0.42
14	Crowded place	-0.78
15	Public transport	-0.02
16	Bus/Train Time table	-1.90
17	Chat with your friends	1.69
18	Recognising faces	0.70
19	Seeing friend in the Playground	-1.06
20	Use playstation	1.04
21	Computer games	0.49
22	Listening to Music	0.65
23	Swimming	0.76
24	Athletics	-0.15
25	Ball games	-0.81

### 4.8.9. Exploratory Endpoints

## Statistical Analysis Plan Template

Sponsor:	ProQR Therapeutics		
Protocol:	PQ-110-002		
Document Version No.:	1.0	Document Date:	04 JAN 2022

### 4.9. Pharmacokinetic Evaluations

It is expected that the vast majority of measured PK concentrations is below limit of quantification (BLQ). Thus, no pharmacokinetic parameters ( $C_{max}$ ,  $T_{max}$ ,  $AUC_{0-24}$ ,  $AUC_{last}$  and  $AUC_{0-inf}$ ) will be derived. All individual measurement results above limit of quantification will be shown in a individual level table, and all measurements – above or below limit of quantification will be presented in the listings on the safety population.

## Statistical Analysis Plan Template

Sponsor:	ProQR Therapeutics		
Protocol:	PQ-110-002		
Document Version No.:	1.0	Document Date:	04 JAN 2022

### 5. CHANGES TO PLANNED ANALYSES

The definition of baseline relevant to PQ-110-001 specified in the protocol has been changed and described in Section 4.2.4 of this SAP.

More precise description with respect to the secondary endpoints are described in Section 2.5.1.2 of this SAP.

The exploratory endpoint “Change in Ellipsoid Zone line by OCT” listed in the protocol which is refer to the same as the secondary endpoint related to OCT has been removed in this SAP. The more detail is described in Section 4.8.4.

The definition of the Efficacy Evaluable Population has been changed from that in specified in the protocol by removing the requirement for at least one post-baseline assessment.

The Pharmacokinetics (PK) Population has been removed since we will not derived pharmacokinetic parameters as it is expected that the vast majority of measured PK concentrations is below limit of quantitation (BLQ).

## Statistical Analysis Plan Template

Sponsor:	ProQR Therapeutics		
Protocol:	PQ-110-002		
Document Version No.:	1.0	Document Date:	04 JAN 2022

## Statistical Analysis Plan Template

Sponsor:	ProQR Therapeutics		
Protocol:	PQ-110-002		
Document Version No.:	1.0	Document Date:	04 JAN 2022

---

### 7. APPENDIX A

This SAP refers to the following documents:

## Statistical Analysis Plan Template

Sponsor:	ProQR Therapeutics		
Protocol:	PQ-110-002		
Document Version No.:	1.0	Document Date:	04 JAN 2022

---

## Statistical Analysis Plan Template

Sponsor:	ProQR Therapeutics		
Protocol:	PQ-110-002		
Document Version No.:	1.0	Document Date:	04 JAN 2022

---

## Statistical Analysis Plan Template

Sponsor:	ProQR Therapeutics		
Protocol:	PQ-110-002		
Document Version No.:	1.0	Document Date:	04 JAN 2022

## Statistical Analysis Plan Template

Sponsor:	ProQR Therapeutics		
Protocol:	PQ-110-002		
Document Version No.:	1.0	Document Date:	04 JAN 2022

---

## Statistical Analysis Plan Template

Sponsor:	ProQR Therapeutics		
Protocol:	PQ-110-002		
Document Version No.:	1.0	Document Date:	04 JAN 2022

---
